**Hyperpolarized Xe-129 MR Imaging**

The patient lies on their back in an MR scanner, and has conventional safety monitoring throughout the scan (direct visual observation, arterial oxygen saturations and heart rate monitoring). They wear a lightweight vest containing the imaging coils over their clothes that is necessary for acquiring images.

Before the first Xe-129 MR scan involving inhalation of up to 1L of xenon, patients will be asked to breath in a small volume of xenon of approximately 100mL mixed with medical grade nitrogen for a total volume of 1L. The patient will be instructed to perform a standard breath hold for a short period of time (approximately 2 seconds). This is a set-up procedure for the scan enabling optimization of Xe-129 MR parameters according to patient height and weight as well as a practice run for the patient. The output from calibration (flip angle measurement) enables the best quality Xe-129 MR images to be acquired for each individual and is not be used to evaluate the study endpoints.

**Hyperpolarized Xenon gas MR Imaging in Radiotherapy**

For the actual Xe-129 MRI scan, the patient breathes out, and then breathes in from a bag containing up to 1L of xenon, balance nitrogen. The total volume of gas participants inhale for Xe-129 MRI scans is 1L, however this may consist of a mixture of 50-100% hyperpolarized xenon and up to 50% nitrogen i.e. 500 mL to 1L of hyperpolarized xenon is mixed with medical grade nitrogen to make up a total volume of 1L. Breathing in xenon is challenging for some people because it has a density 4.55 time greater than air, which increases airways resistance (72). Therefore patients are sometimes given assistance with the respiratory manoeuvre by physically compressing the bag during inhalation. The patient receives a bag full of air or oxygen to practice this breathing manoeuvre before breathing xenon. Scanning then takes place during a breath hold for approximately 20 seconds, or during an inhalation-exhalation manoeuvre. This manoeuvre with scanning will be repeated up to four times to enable acquisition of all Xe-129 MRI sequences. The four inhalations may be different sequences or the same sequence may be repeated to assess reproducibility. There are currently three confirmed sequences (ventilation, ADC and dissolved phase) with further sequences under technical development that will be introduced during the course of the study period.

If the patient fails to breathe in sufficient xenon at the required time, the investigator may suggest that the procedure is repeated once or twice. One patient will not exceed six inhalations of xenon in a single day. In the unlikely occurrence of an adverse event, a radiographer will be able to access the participant immediately. Participants are monitored for at least 30 minutes after the final hyperpolarized xenon dose before they are discharged home. It is likely approximately 3 hours will have elapsed since administration of the first hyperpolarized xenon dose by this time. Participants will receive a telephone consultation 24 hours after completion of hyperpolarized Xe-129 MRI to review any AEs that have occurred in the interim following discharge. Furthermore, participants will attend hospital and see the Oncology clinical team on a daily basis during radiotherapy when they will have the opportunity to report any AEs relating to hyperpolarized Xe-129 gas. The study schedule includes follow-up by both the study team and Oncology clinical team in out-patient clinic at regular intervals throughout the 9 month trial duration. This will allow for review of possible AE/SAE two weeks after each hyperpolarized xenon scanning session.

Following the final xenon administration at the 3-month post-radiotherapy follow-up visit, participants will also receive a telephone consultation two weeks later to review AE/SAEs.

Hyperpolarized Xe-129 MR imaging will be performed using xenon hyperpolarized by a xenon hyperpolarizer (Polarean 9880) and imaged on a 1.5T MRI scanner. A dedicated Xe-129 chest coil will be used. Images will be obtained in the coronal plane. During each scanning session, up to four hyperpolarized Xe-129 MR sequences will be acquired with the participant undergoing four separate xenon breath holds. Hyperpolarized Xe-129 MR will be repeated at baseline to assess reproducibility. Total scanning time will be approximately half a day during each visit. The participant will spend a total of approximately 1 ½ hour within the MRI scanner during each visit. Image acquisition strategy will include:-

- Short echo proton MRI for co-registration purposes.

**Hyperpolarized Xenon gas MR Imaging in Radiotherapy**

- Static ventilation
- Dynamic ventilation.
- Diffusion Imaging (ADC).
- Intrapulmonary PO2
- Dissolved phase imaging.

If the study team fails to acquire all the required Xe-129 MRI sequences during a single scanning session as a result of technical difficulties or non-synchronisation of patient breathing and scanning, the patient may be requested to return within a few days to complete Xe-129 lung MRI scanning and ensure acquisition of all sequences for that study visit. This may take up to half a day and may involve repeating one or two Xe-129 MR sequences previously acquired since these cannot be analysed accurately if they have not all been performed at the same time point.

**Gadolinium enhanced lung MRI**

This will be performed on a 1.5T MRI scanner according to local standard protocols. An injection containing gadolinium is given via the cannula (this will be the same one used for nuclear medicine and CT scans) and lung MRI carried out during a short breath hold. Since patients do not need to move from the bed following Xe-129 lung MRI there is minimal inconvenience and disruption for the patient.

**Description of MultiHance (gadolinium injection)**

MultiHance contains gadolinium, which is a rare earth metal that improves images of pulmonary arteries during lung MRI. Gadolinium is given in the form of gadobenate dimeglumine. The dose of MultiHance is around 0.2 ml/ kg body weight. There is no interaction or interference between MultiHance and inhalation of hyperpolarized Xe-129 gas, allowing this study measure to be performed straight after the hyperpolarized Xe-129 MRI scan safely.

**Safety considerations for MultiHance**

MultiHance is commonly used in clinical practice for perfusion imaging during MRI where it is safe and well tolerated. Common side effects (more than 1/100 but fewer than 1/10) are headache,

**Hyperpolarized Xenon gas MR Imaging in Radiotherapy**

nausea, feeling hot and local reactions such as swelling or pain at the injection site. Rarely (more than 1/ 10,000 but fewer than 1/ 1,000) allergic reactions can arise leading to shock, itching, skin rashes, urticarial, fainting, a swollen face and neck and wheezing, or other serious effects including tinnitus, pancreatitis, pulmonary oedema, intracranial hypertension or hemiparesis.

**9.6. Baseline assessment for patients with diagnoses other than lung cancer**

Patients with diagnoses other than lung cancer, for example, oesophageal cancer, chest wall tumours and lymphoma will undergo the following baseline assessments only: -

- Arterial oxygen saturations (SaO2)
- Dyspnoea
- Radiation-induced lung toxicity (RILT)
- Hyperpolarized Xe-129 MR Imaging

Full details about each of the study measures has been provided above in Section 9.5.

**9.7. Radiotherapy**

Radiotherapy treatment will be CT planned and delivered as per local departmental radiotherapy protocols. The treating Oncologist will not have access and be blinded to the baseline Xe-129 MRI images whilst planning radiotherapy. Entry into this study will not delay patients commencing radiotherapy, and their treatment will not be altered as a result of their enrolment into this study.

The appropriate beam energy will be selected to optimize the RT dose distribution in the target volume and minimize dose to non-target tissues.

**9.8. Subsequent Visits for patients with a diagnosis of lung cancer**

At each hospital visit, study patients will be asked whether they have had any:

- Hospitalisations
- Consultations with other medical practitioners
- Disability or incapacity or other adverse event that has occurred since their last visit

All study measures will be performed and analysed as detailed previously in sections 9. and 12. of this document.

Although all three follow-up visits will be offered to participants, only one visit post-commencement of radiotherapy will be compulsory.

**Half-way through radiotherapy schedules**

**Hyperpolarized Xenon gas MR Imaging in Radiotherapy**

The only study measure to be completed will be hyperpolarized Xe-129 MR imaging involving up to a maximum of six xenon breath holds. Adverse events and serious adverse events will be reviewed.

**Final day of treatment and 3-months following completion of radiotherapy: -**

- AE/SAE review
- Arterial oxygen saturation
- Dyspnoea & CTCAE version 4 RILT assessment
- Full pulmonary function tests
- Thoracic CT
- Hyperpolarized Xe-129 MR imaging involving up to a maximum of six xenon breath holds
- Gadolinium enhanced lung MRI

**Two weeks after final xenon administration at 3-month post-radiotherapy**

- AE/SAE review via telephone consultation

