## 7. TRIAL DESIGN

### 7.1. Summary of Study Design

This will be an open, single-centred study in the UK. The study group will include 30 patients who are considered suitable for radiotherapy that will affect the lung. Participants considered for radiotherapy that will affect the lung include those with a diagnosis of lung cancer and those with other diagnoses, for example, oesophageal cancer, chest wall tumours and lymphoma. All potential participants for this study undergo an *enrolment visit* (Visit 1). This is an opportunity to discuss the study in more detail, and for those choosing to take part to gain informed, written consent. Eligibility criteria will be checked. All female participants of child-bearing age will have had pregnancy excluded as part of their routine clinical care in Oncology prior to starting radiotherapy. Volunteers will be invited to undertake a 'dummy run' of Xe-129 lung MRI imaging, during which they lie on a couch similar to that used during the MRI, and practice the manoeuvre required when breathing in xenon from a 1L bag during subsequent lung imaging. During the dummy run this will simply be air or oxygen in the 1L bag.

The enrolment and baseline visits are compulsory for all participants. Participants will be required to complete at least one follow-up visit from the "half-way through" following commencement of radiotherapy, end of treatment and 3-months post-radiotherapy visits. The three follow-up visits will be offered to all patients, however completion of only one visit post-commencement of radiotherapy will be compulsory.

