**Hyperpolarized Xenon gas MR Imaging in Radiotherapy**

[figure not shown]
All patients enrolled with lung cancer will undergo clinical assessment involving objective physiological measures (pulmonary function testing and pulse oximetry) and patient orientated functional measures (dyspnoea scores, CTCAE version 4. Radiotherapy-induced lung toxicity assessment) at baseline, on the final day of radiotherapy treatment and 3 months post treatment. These assessments will not be completed at the two week following commencement of radiotherapy schedule visit.

Patients to be treated with radiotherapy affecting the lung that do not have lung cancer, such as oesophageal cancer, chest wall tumours, lymphoma affecting the mediastinum and others, will undergo clinical assessment (excluding full pulmonary function testing) and Xe-129 lung MRI imaging only at each visit.

[figure not shown]
Participation in these full tests takes up to a day, allowing patients time to rest between tests. All participants will be monitored for at least 30 minutes after the final hyperpolarized xenon dose before they are discharged home. It is likely approximately 3 hours will have elapsed since administration of the first hyperpolarized xenon dose by this time. Participants will receive a telephone consultation 24 hours after completion of hyperpolarized Xe-129 MRI to review any AEs that have occurred in the interim following discharge. Furthermore, participants will attend hospital and see the Oncology clinical team on a daily basis during radiotherapy when they will have the opportunity to report any AEs relating to hyperpolarized Xe-129 gas. The study schedule includes follow-up by both the study team and Oncology clinical team in out-patient clinic at regular intervals throughout the 9 month trial duration. This will allow for review of possible AE/SAE two weeks after each hyperpolarized xenon scanning session.

Following the final xenon administration at the 3-month post-radiotherapy follow-up visit, participants will also receive a telephone consultation two weeks later to review AE/SAEs.

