**9.11. Definition of End of Trial**

The end of trial is the date of the last hospital visit of the last participant.

**Hyperpolarized Xenon gas MR Imaging in Radiotherapy****10. INVESTIGATIONAL MEDICINAL PRODUCT (IMP)****10.1. IMP Description**

No treatments are given as a part of the proposed study since the appropriate radiotherapy schedule is taking place as part of patients' routine clinical care.

Hyperpolarized Xe-129 lung MRI requires breathing in an investigational medical product, hyperpolarized xenon gas, Xe-129, which is described in detail below.

Xenon is an inert gas that is present in the atmosphere in low concentrations. It has no smell or taste. Breathing xenon or undergoing an MRI scan does not involve exposure to ionising radiation. We will administer a maximum of 6 x 1 Litre doses of hyperpolarized xenon gas to each participant per hospital visit for Xe-129 lung MR imaging. If it is not essential to give 100% xenon for imaging, the gas may be diluted with ultrapure nitrogen. The ratio of xenon to nitrogen will vary from 10% to 100% but the volume provided to the patient will always be 1 L.

The route of administration is inhalation. All female participants of child-bearing age will have had pregnancy excluded as part of their routine clinical care in Oncology prior to starting radiotherapy.

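### The two-week safety call is triggered only by xenon at the optional 3-month visit, so a participant whose last xenon is earlier has no scheduled two-week call; the call can also fall after the defined end of trial

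*Combined protocol and SAP*

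**What the plan says.** **The two-week call.** The follow-up schedules in 9.8 (lung cancer) and 9.9 (other diagnoses) each end with a telephone AE/SAE review under the heading "Two weeks after final xenon administration at 3-month post-radiotherapy". Sections 7.1, 9.5 and 10.1 describe the same call: after the xenon given at the 3-month visit, "participants will also receive a telephone consultation two weeks later to review AE/SAEs".

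**Status of the 3-month visit.** Section 7.1 offers all three follow-up visits to everyone but states that "completion of only one visit post-commencement of radiotherapy will be compulsory". Sections 9.8 and 9.9 repeat that "only one visit post-commencement of radiotherapy will be compulsory".

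**The statement about every session.** Sections 7.1, 9.5 and 10.1 describe "follow-up by both the study team and Oncology clinical team in out-patient clinic at regular intervals" over the 9 months and conclude: "This will allow for review of possible AE/SAE two weeks after each hyperpolarized xenon scanning session". They add that participants will "see the Oncology clinical team on a daily basis during radiotherapy", and that there is a telephone call 24 hours after each Xe-129 MRI.

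**End of trial.** Section 9.11 reads: "The end of trial is the date of the last hospital visit of the last participant".

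**The concern.** The call is worded as though the 3-month session were always the last xenon exposure. Once that visit is optional, the last exposure can come at the half-way visit, on the final day of radiotherapy or, for someone who withdraws early, at baseline. Followed as written, the plan then prompts no two-week call, although the text presents a two-week review as available after every session.

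This matters for how late events are found. Under 11.3, all adverse events are recorded up to 24 hours after a scan. After that, only events that the chief investigator judges possibly related to xenon, or medically important, are reported. Finding a later reaction therefore depends partly on someone asking the participant at a known time. A participant who does not return has no later study visit at which the question would be put.

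The end-of-trial definition raises a separate problem: a required safety contact can fall after the trial has formally ended.

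**Working it through.** No sample size, power or event figure is involved. The check is a comparison of the sections and a count of the permitted attendance patterns.

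**1. Which sessions have a dated two-week contact in 9.8 and 9.9?** There are four xenon visits.

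| Xenon session | Dated two-week contact in 9.8/9.9 | Other routes named in 7.1, 9.5 and 10.1 |
|---|---|---|
| Baseline (Visit 2) | None | 24-hour call; daily oncology contact once radiotherapy is under way; clinic at unstated intervals |
| Half-way (Visit 3) | None | 24-hour call; daily oncology contact while radiotherapy continues; clinic at unstated intervals |
| Final day (Visit 4) | None | 24-hour call; clinic at unstated intervals |
| 3 months (Visit 5) | Telephone call | 24-hour call; clinic at unstated intervals |

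**2. Which attendance patterns trigger the call?** A participant must complete at least one of Visits 3, 4 and 5.

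- Permitted patterns: 2³ − 1 = 7.
- Patterns that include Visit 5: 2² = 4. These trigger the call.
- Patterns without Visit 5: 7 − 4 = 3, namely Visit 3 only, Visit 4 only, and Visits 3 and 4. These do not.
- Withdrawal after baseline lies outside the seven and does not trigger the call either.

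These are counts of patterns, not of participants.

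**3. What covers the three patterns without the call?**

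- Visit 3 only: daily oncology contact reaches two weeks only if at least two weeks of radiotherapy remain. Schedules follow local protocols and their length is not given.
- Visit 4 only, and Visits 3 and 4 (two of the three): the last xenon is given on the day radiotherapy ends, so the daily contact does not extend over the following two weeks. After the 24-hour call, the remaining route is clinic follow-up with no stated timing.

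Participants who attend Visits 4 and 5 do receive the call after Visit 5. For their final-day session, however, the next contact listed in 9.8 or 9.9 is the 3-month visit.

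**4. How many participants?** The number without a call after their last xenon is 30 × (1 − proportion attending Visit 5). No attendance rate is given, so the result can lie anywhere from 30 × 0 = 0 to 30 × 1 = 30.

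**5. End of trial.** Suppose the last participant's last hospital visit is the 3-month visit, on day D. Section 9.11 ends the trial on day D; 9.8 and 9.9 place the call at D + 14 days. The call therefore falls 14 days after the defined end.

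**The case against.** The strongest reply is that a review route exists for every session. The text says that follow-up will allow for a two-week review, which is weaker than promising one, and it names the means: out-patient clinic with both teams, plus daily oncology contact during radiotherapy. The telephone call is described as additional. This stands. A reader might infer that participants who finish early have no two-week review at all, or that the protocol guarantees one for every session; neither follows. What is missing is a date, not every possible contact.

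The study schedules in 7.2 are flow charts that are not shown in the available text. They might contain a dated contact, so its absence from the whole plan cannot be confirmed. Sections 9.8 and 9.9 would still need to agree with them.

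Other safety capture also limits the consequences:

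- Each later visit asks about events since the last one (9.8, 9.9).
- Possibly related or important events remain reportable after 24 hours with no end date (11.3).
- SAEs following scanning are reportable with no stated cut-off (11.4).
- Participants withdrawn because of an adverse event are followed until it resolves or stabilises (9.10).
- Xenon effects are described as lasting minutes (10.1, 11.5).

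All of this stands. It means that the safety summary would not come mainly from those who reach 3 months, as a reader might infer: scan-day and 24-hour data come from every scanned participant who can be contacted, whatever their later attendance. Nor do the documents show that those who miss the 3-month visit are sicker or tolerate scanning less well.

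On the end of trial, 12.4 ends the study after follow-up is complete, and 12.7 stops observation at termination. Read together, these can include the call. Only 9.11 conflicts with it.

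**Conclusion.** The point holds in a limited form. A two-week review is described as possible after each xenon session, but in 9.8 and 9.9 it is dated only for the 3-month session, which participants may skip. Three of the seven permitted attendance patterns, and withdrawal after baseline, leave a participant with no scheduled two-week call after the last xenon. The gap is clearest when that xenon is given on the final day of radiotherapy. Separately, 9.11 closes the trial before a call that follows a last visit at 3 months.

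The conclusion assumes that the 7.2 flow charts show no further dated contact and that the last hospital visit in 9.11 means a study visit. The number of participants affected cannot be estimated from the documents. The matter concerns safety follow-up and does not touch the primary imaging comparison. It is worth correcting because the correction is cheap and uses the protocol's own interval. A reader might go further and ask for an extra mandatory call for everyone after the final-day session. That is a preference about monitoring intensity; the documents require only that the contact delivering the review be identified.

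**What to change.** 1. In 7.1, 9.5, 9.8, 9.9 and 10.1, trigger the existing two-week telephone AE/SAE review from each participant's last xenon administration, at whichever visit that occurs. Include participants who withdraw, unless they withdraw consent to contact.
2. Reconcile the every-session statement in 7.1, 9.5 and 10.1 with the lists in 9.8 and 9.9 by naming the dated contact that delivers the two-week review after the final-day session. State where it is recorded. An existing clinic appointment may serve. Check the 7.2 flow charts against the result.
3. In 9.11, define the end of trial as the last participant's last safety contact, and align 12.7 so that observation plainly includes the call.

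The cost is wording changes and at most about one telephone call per participant, or about 30 × 1 = 30 calls, some of which the plan already includes for those who attend at 3 months. No scan or hospital visit is added.

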**9.9. Subsequent Visits for patients with a diagnosis other than lung cancer**

At each hospital visit, study patients will be asked whether they have had any:

- Hospitalisations
- Consultations with other medical practitioners
- Disability or incapacity or other adverse event that has occurred since their last visit

All study measures will be performed and analysed as detailed previously in sections 9. and 12. of this document.

Although all three follow-up visits will be offered to participants, only one visit post-commencement of radiotherapy will be compulsory.

